#### **13.3.1.3. Outcome: Papilloedema measured by OCT (optic nerve head size, retinal nerve fibre layer)**

##### **13.3.1.3.1. Intercurrent event: ICP-lowering medications**

All patients will suffer from papilloedema at enrolment as it is the hallmark feature of the disease [Wall, 2014; Ottridge, 2017; Markey, 2020]. If a patient takes ICP-lowering medication, it is logical to expect that their ICP will decrease and that the papilloedema will reduce in turn. As stated, we expect ICP-lowering medication use to be greater in the placebo arm. Outcomes from patients that take these medications will confound the estimation of the causal treatment effect of Presendin. For these reasons, we propose to remove the OCT outcomes following the administration of ICP-lowering medications and replace these observations with imputations generated by a method suitable for longitudinal data imputation. Outcomes recorded at the unscheduled visit when the treatment failure is confirmed (and just prior to starting ICP lowering medication) will be defined as the last analysed visit. This will allow estimation of the treatment effect that is purely and causally attributable to Presendin.

##### **13.3.1.3.2. Intercurrent event: Off-protocol lumbar punctures**

As discussed above, LPs are a material and widespread intervention in the treatment of IIH, given with the intention of reducing intracranial pressure and improving the

Study Number: INVEX-CLIN-IIH-301 Protocol	Compound No.: Presendin
	Version: 3.0

associated symptoms of the disease, including reducing pressure on the optic nerve and papilloedema. Patients that have LPs are expected to experience less pressure on the optic nerve and therefore relatively less papilloedema. Beneficial effects dissipate with time and whilst there has been no longitudinal assessment to quantify papilloedema after an LP the consensus of clinicians would predict that effects of the LP on papilloedema would have dissipated by one month. Outcomes from patients that have undergone off-protocol LPs will confound the estimation of the causal treatment effect of Presendin. OCT outcomes will be recorded repeatedly during the trial. For the reasons stated, we propose to remove OCT outcomes recorded in the 4-weeks following an off-protocol LP, and replace these observations with patient-within-arm imputations generated by a method suitable for longitudinal data imputation.

#### **13.3.1.3.3. Intercurrent event: Dramatic weight-loss**

Research has shown that weight loss in IIH is associated with reductions in IIH symptoms, including decreases in papilloedema [Sinclair, 2010]. Sudden dramatic weight loss, e.g. arising from a surgical procedure will likely yield material changes to IIH symptoms. This will confound the estimation of the causal treatment effect of Presendin. For these reasons, we propose to remove OCT outcomes of patients that experience weight loss exceeding 10% of baseline weight after a surgical weight-loss procedure from the date of procedure. These outcomes will be replaced with patient-within-arm imputations generated by a method suitable for longitudinal data imputation.

#### **13.3.1.4. Outcome: Monthly headache days (MHD)**

##### **13.3.1.4.1. Intercurrent event: Headache-preventative medications**

The great majority of patients are expected to suffer from headache because it is a common symptom of the disease [Wall, 2014; Ottridge, 2017; Markey, 2020]. If a patient takes medication that is intended to prevent headache, it is logical to expect that their headache burden will be decreased. Despite the widely-observed short-term placebo-effect observed in headache outcomes, we expect headache-preventative medication use to be greater in the placebo arm. Outcomes from patients that take headache-preventative medications will confound the estimation of the causal treatment effect of Presendin (more so with botulinum toxin A and CGRP therapies). For these reasons, we propose to remove the headache outcomes following the administration of headache-preventative medications and replace these observations with imputations generated by a method suitable for longitudinal data imputation. This will allow estimation of the treatment effect that is purely and causally attributable to Presendin. Patients who require a change to their headache preventative medications will do this through consultation with the IAC and such a change would be regarded as headache rescue therapy.

Study Number: INVEX-CLIN-IIH-301 Protocol	Compound No.: Presendin
	Version: 3.0

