14. Allergy/known hypersensitivity to the active substance and/or excipients of the investigational product
15. Has known contraindications to glucagon like peptide-1 (GLP-1) receptor agonists (e.g., ketoacidosis, severe gastrointestinal disease, pancreatitis, renal impairment) which may affect the safety of the patient
16. Using any glucose-lowering medication
17. Currently taking warfarin

Study Number: INVEX-CLIN-IIH-301 Protocol	Compound No.: Presendin
	Version: 3.0

18. Alanine transaminase (ALT) or aspartate transaminase (AST)  $\geq 2x$  the upper limit of normal (ULN), total bilirubin  $\geq 1.5x$  ULN, or alkaline phosphatase (ALP)  $\geq 1.5$  ULN at screening (Note – patients with elevated total bilirubin are not excluded if they meet criteria for Gilbert’s syndrome, including: bilirubin is predominantly indirect [with normal direct bilirubin level]; and ALT, AST and ALP  $\leq 1x$  ULN)
19. Kidney disease (as defined by serum cystatin C-based estimated glomerular filtration rate [eGFR]  $< 55$  mL/min/1.73 m^2, calculated at investigator site)
20. Any of the following abnormalities in clinical laboratory tests at screening, as assessed by the central laboratory and confirmed by a single repeat, if deemed necessary: *Hemoglobin*  $< 10$  g/dL ( $< 100$  g/L); *Platelet count*  $< 75 \times 10^9/L$  ( $< 75,000/mm^3$ )
21. Using recreational or illicit drugs at the time of signing the informed consent, or recent history (within the last year) of drug or alcohol abuse or dependence according to the DSM-5 criteria, that in the opinion of the investigator puts the patient at risk
22. Is unable to self-administer the trial medication (or unable to administer trial medication with support) after receiving training during the Screening period
23. History of any clinically significant disease or disorder that, in the opinion of the investigator, may either put the patient at risk because of participation in the trial or influence the results or the patient’s ability to participate in the trial
24. Any contraindication to lumbar puncture procedure in the opinion of the investigator
25. Has participated in any other interventional trial within 1 month prior to the screening visit.
26. Is pregnant or breastfeeding

Note: Use of headache preventative medication is allowed at enrolment (except for Topiramate). Changes to headache preventative medication during the trial should be made in consultation with the IAC – see section [10.1.2](#)

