##### **6.3.3.1. Headache Preventative Medication Review**

A review of any headache preventative medications taken by the patient will be undertaken at each clinic visit. If the Investigator alters the headache preventative medication, this will be considered rescue medication (Section 10.1.1) and the IAC consulted. Use of headache preventative medication will be recorded at trial visits as outlined in the Time and Events table (Table 1).

Patients will record their acute headache analgesic use in their trial diary.

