## **10.2. Prohibited Medications**

### **10.2.1. Prior to screening and randomisation**

- Treatment to lower ICP within 1 week prior to screening (e.g., acetazolamide, topiramate (including if used as a migraine preventative), diuretics, glucocorticoids (I.V., injectable steroids or oral (including dexamethasone and prednisolone)). (Nasal, inhaled, or topical steroids are allowed).
- Exposure to fluoroquinolones, lithium, vitamin A, or tetracyclines within 2 months of diagnostic LP
- Glucagon like peptide-1 receptor agonist within last 4 weeks prior to screening
- Warfarin
- Glucose-lowering medication COVID-19 vaccine within 2 weeks prior to screening
- Recreational or illicit drugs during screening period

Note: Use of headache preventative medication is allowed at enrolment (except for Topiramate). Changes to headache preventative medication during the trial should be made in consultation with the IAC – see section [10.1.2](#).

Study Number: INVEX-CLIN-IIH-301 Protocol	Compound No.: Presendin
	Version: 3.0

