### 13.3.1. Estimands

We have specified intercurrent events that are material to the measurement of our primary and secondary outcomes, and unbiased estimation of treatment effects attributable to Presendin.

ICP-lowering medication include: acetazolamide, topiramate, diuretics, glucocorticoids (oral dexamethasone and oral prednisolone). Headache-preventative medications include: amitriptyline, topiramate, nortriptyline, beta blockers, candesartan, sodium valproate, pizotifen, botox, CGRP-therapy.

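### Version 3.0's headache intercurrent-event rule is triggered by taking a preventative, not by starting or changing one; read literally, it removes all post-baseline headache data from patients on a permitted, stable preventative

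*Protocol*

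**What the plan says.** All references are to protocol Version 3.0 unless stated.

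- **Removal rule (13.3.1.4.1).** "we propose to remove the headache outcomes following the administration of headache-preventative medications and replace these observations with imputations". The stated reason is that "Outcomes from patients that take headache-preventative medications will confound the estimation of the causal treatment effect of Presendin", together with the expectation that such use will be more frequent on placebo.
- **Drugs counted (13.3.1).** "Headache-preventative medications include: amitriptyline, topiramate, nortriptyline, beta blockers, candesartan, sodium valproate, pizotifen, botox, CGRP-therapy".
- **Eligibility (notes in the Protocol Summary, 5.2.2 and 10.2.1).** "Use of headache preventative medication is allowed at enrolment (except for Topiramate"). The note in 10.2.1 adds: "Changes to headache preventative medication during the trial should be made in consultation with the IAC".
- **What counts as headache rescue.** The last sentence of 13.3.1.4.1 speaks of patients who need a change of preventative and says "such a change would be regarded as headache rescue therapy". Section 6.3.3.1 agrees: "If the Investigator alters the headache preventative medication, this will be considered rescue medication". Section 10.2.2 says the same for use during the trial.

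**The concern.** The permission and the removal rule do not fit together. A patient may enter on, say, amitriptyline and stay on the same dose. Nothing has happened to that patient after randomisation that could distort the treatment comparison, yet each diary month comes after an administration of a listed drug. Under the sentence as it stands, all of that patient's post-baseline headache data are set aside and imputed.

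This would discard observed data that are comparable between arms and replace them with model output. It also leaves two defensible datasets, one from the literal sentence and one from the apparent intent. Section 13 requires the SAP to be final only before database lock. Monthly headache days is the outcome named in the heading of 13.3.1.4. The rule's broader reference to headache outcomes plausibly also reaches moderate to severe headache days, the responder rates, severity and analgesic days.

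**Working it through.** The protocol gives no figure on this point: Version 3.0 is powered on ICP and PMD (13.2.1) and states no power for headache days. The check is therefore a comparison of text, followed by an illustration of size.

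**Step 1: who meets the trigger.** The removal sentence requires administration of a preventative. It does not require that the drug be new, added or altered after randomisation. The permission in 5.2.2 and 10.2.1 covers every listed drug except topiramate. A patient continuing any of the others meets the trigger from the first post-baseline day to the last.

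**Step 2: does the rationale cover these patients?** The rationale expects more use on placebo. That can hold for drugs started after randomisation in response to poor control. Use at entry is fixed before allocation, so randomisation balances it in expectation. The reason given for removal does not apply to it.

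**Step 3: comparison with the neighbouring rules for the same outcome.**

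- ICP-lowering drugs (13.3.1.4.4): barred for a week before screening and treated as rescue in the trial, so taking one is a post-baseline event; a last analysed visit is also named.
- Off-protocol lumbar puncture (13.3.1.4.2): removal limited to four weeks.
- Surgical weight loss (13.3.1.4.3): removal runs from the date of the procedure.
- Headache preventatives (13.3.1.4.1): neither a post-baseline starting point nor an end.

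**Step 4: size, for an assumed share f enrolled on a listed preventative.** The documents do not give f. With 240 randomised patients (13.2.1), patients removed = 240 × f and patients retained = 240 × (1 − f). If imputation recovers no information and data are otherwise complete, the standard error rises by the factor 1/√(1 − f).

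| Assumed f | Removed | Retained | SE factor |
|---|---|---|---|
| 10% | 24 | 216 | 1.054 |
| 20% | 48 | 192 | 1.118 |
| 30% | 72 | 168 | 1.195 |
| 40% | 96 | 144 | 1.291 |
| 50% | 120 | 120 | 1.414 |

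For example, at f = 20%, √(240/192) = 1.118. If the event were restricted to a start or change after randomisation, the number losing data through stable baseline use would be 0 of 240.

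**The case against.** The best defence is that the sponsor meant a change of preventative. The rule sits under a heading for intercurrent events, which normally means events after treatment starts. The placebo-arm rationale fits only post-randomisation use, and the paragraph ends by naming a change. That is a fair account of the probable intent, and it stands: a reader might infer that total loss is what the sponsor plans, and the documents do not show that. It does not rescue the operative sentence, which a programmer could follow to the letter.

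It can also be said that such detail belongs in the SAP. Onset dates and the imputation model do. The trigger, however, is fixed here in the protocol, and fixed too widely.

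Four further inferences are tempting but not supported:

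- *That a beta blocker or candesartan taken for blood pressure triggers removal.* The rationale in 13.3.1.4.1 concerns drugs taken with the aim of preventing headache. The list in 13.3.1 carries no indication qualifier, so this needs clarifying, but it is not an established consequence.
- *That affected patients would be imputed from patients not on preventatives.* The section asks only for a method suited to longitudinal data; the source is not stated.
- *That Version 3.0 broke a rule that worked in Version 1.0.* Version 1.0 did have patients agree to forgo preventatives, but its exclusion criteria barred only recent botulinum toxin, CGRP injections and nerve blocks, not oral preventatives. The tension was partly there already.
- *That the trial's main result is at risk.* The ICP primary endpoint is untouched.

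**Conclusion.** The point holds as a defect in a stated rule: in Version 3.0 the removal trigger contradicts the enrolment permission and is wider than the protocol's own definition of headache rescue. Read literally, it costs patients on a stable permitted preventative all their post-baseline headache data. The conclusion rests on the wording alone.

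The size is not known. The range of 24 to 120 of 240 patients depends on an assumed 10% to 50% entering on a preventative, and the standard-error factors are upper illustrations because they give imputation no credit. The effect is confined to secondary and exploratory headache endpoints. The file also holds appendices headed Version 4.0 without the body of that version, so a later correction cannot be ruled out.

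**What to change.** In 13.3.1.4.1, and in the SAP to match:

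- define the intercurrent event as the start of a headache preventative, or a change of its drug or dose, after randomisation;
- remove headache outcomes only from the date of that start or change;
- state that outcomes under a preventative already in stable use at baseline are kept;
- state that a listed drug counts only when it is taken to prevent headache.

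Adjusting for baseline preventative use is an option, not a condition of the repair.

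The cost is wording. Preventative use is reviewed at Visits 1 and 2 (6.1.1, 6.1.2), and start date, dose and reason for use are recorded (10.1), so no new data are needed. Check the Version 4.0 text of this section before drafting.

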#### **13.3.1.4.2. Intercurrent event: Off-protocol lumbar punctures**

As discussed above, LPs are a material and widespread intervention in the treatment of IIH, given with the intention of reducing intracranial pressure and improving the associated symptoms of the disease, including reducing the frequency and intensity of headache. Beneficial effects dissipate with time. Prospective data documents alterations in headache for at least 7 days and whilst there is no prospective longitudinal data over a longer time period consensus amongst clinicians would widely acknowledge that headache in some individuals can be influenced for up to a month [Yiangou, 2019]. Outcomes from patients that have undergone off-protocol LPs will confound the estimation of the causal treatment effect of Presendin. MHD outcomes will be recorded daily via diaries. For the reasons stated, we propose to remove MHD outcomes recorded in the 4-weeks following each off-protocol LP and replace these observations with patient-within-arm imputations generated by a method suitable for longitudinal data imputation.

#### **13.3.1.4.3. Intercurrent event: Dramatic weight-loss**

Research has shown that weight loss in IIH is associated with reductions in IIH symptoms, including decreases in headache frequency and severity [Sinclair, 2010]. Sudden dramatic weight loss, e.g. arising from a surgical procedure will likely yield material changes to IIH symptoms. This will confound the estimation of the causal treatment effect of Presendin. For these reasons, we propose to remove MHD outcomes of patients that experience weight loss exceeding 10% of baseline weight after a surgical weight-loss procedure from the date of procedure. These outcomes will be replaced with patient-within-arm imputations generated by a method suitable for longitudinal data imputation.

#### **13.3.1.4.4. Intercurrent event: ICP-lowering medications**

All patients are expected to suffer from some visual field loss at enrolment because it is the hallmark feature of the disease [Wall, 2014; Ottridge, 2017; Markey, 2020]. If a patient takes ICP-lowering medication, it is logical to expect that their ICP will decrease and that headache will reduce as a result. As stated, we expect ICP-lowering medication use to be greater in the placebo arm. Outcomes from patients that take these medications will confound the estimation of the causal treatment effect of Presendin. For these reasons, we propose to remove the MHD outcomes following the administration of ICP-lowering medications and replace these observations with imputations generated by a method suitable for longitudinal data imputation. Outcomes recorded at the unscheduled visit when the treatment failure is confirmed (and just prior to starting ICP lowering medication) will be defined as the last analysed visit. This will allow estimation of the treatment effect that is purely and causally attributable to Presendin.

Study Number: INVEX-CLIN-IIH-301 Protocol	Compound No.: Presendin
	Version: 3.0

**13.3.1.5. Primary Estimand (Hypothetical assuming no concurrent procedures, irrespective of adherence to treatment)**

The primary estimand is defined as the following for the primary endpoint:

- Treatment difference in ICP measurement between Presendin and placebo at Week 24 for all patients who are randomised and start treatment, regardless of adherence to randomised treatment, where patients did not have medications or procedures likely to materially affect ICP.

The primary estimand for the initial secondary endpoint will be handled similarly to the primary endpoint using the “Hypothetical” approach. The initial secondary endpoint is defined as:

- Treatment difference in PMD between Presendin and placebo over 24-weeks for all patients who are randomised and start treatment, regardless of adherence to randomised treatment, where patients did not have medications or procedures likely to materially affect PMD.

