### 13.2.1.1. Perimetric Mean Deviation Power

We summarise here the estimated power for detecting differences between arms in the PMD outcome measure. In the NORDIC trial [Wall, 2014], the authors observed that the improvement from baseline to 6-months in PMD was 0.71dB greater in the experimental arm than the control arm. Cross-sectional SD of PMD was 1.1-1.2 at baseline. Table 2 in their publication shows that the standard error of mean PMD is higher at 6m than at baseline, likely reflecting a combined effect of missing data at 6-months and greater variability of post-baseline measures. We plan to take repeated measures of PMD at baseline, 2 weeks, 1-month (m), 2m, 3 m, 4m, 5m and 6m. Assuming that the overall SD of PMD scores is 1.8, thus introducing some reasonable inflation on Wall *et al.*'s baseline variability parameter for the reasons identified, using the formula given on p.31 of Diggle, Liang & Zeger (1994) we would expect to require 142 patients in total to detect a difference of 0.71dB (justified below) with 90% power at a 5% significance level, if the serial correlation between repeated measures is 0.4 (and we expect a value in this region) [Diggle, 1994]. If the serial correlation parameter is as low as 0.3, the required sample size increases to 166.

Study Number: INVEX-CLIN-IIH-301 Protocol	Compound No.: Presendin
	Version: 3.0

Note that the method used above assumes full follow-up and data collection. Although every effort will be made to collect all outcomes, naturally some missing data is expected. If we inflate the maximum sample size identified above by up to 30% to account for some data loss, we require up to  $166 / 0.7 = 237$  patients. The assumed 30% missing data rate was adjudged to be realistic by the Sponsor based on previous trials in IIH. Thus, we expect to be able to cover the impact of missing data using the extra patients necessitated by the sample size calculation for ICP.

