### **13.2.3. Sample Size Sensitivity**

#### **13.2.3.1. Clinically Meaningful Effect Sizes**

Minimally relevant effect sizes have not been fully determined in IIH given it is a rare disease with relatively few previous trials.

The ICP diagnostic threshold in IIH is 25 cm CSF [Mollan, 2018]. However, it is not necessary to reduce ICP <25 cm CSF to achieve remission from signs and symptoms of IIH in all patients [Sinclair, 2010]. The clinical importance of a particular change in ICP

Study Number: INVEX-CLIN-IIH-301 Protocol	Compound No.: Presendin
	Version: 3.0

will vary depending on the starting ICP and the impact this pressure has on vision and headache. Changes in ICP of 5 cm CSF are generally considered meaningful when treating IIH patients. For example, in a clinical study evaluating the benefits of weight loss in IIH patients, a 16.5% (6.2 cm CSF) reduction in ICP resulted in a statistically significant improvement in headache and vision measures as well as quality of life [Sinclair, 2010]. In the IIH Treatment trial (n=165), a study evaluating the drug treatment acetazolamide against placebo, a reduction of -5.9 cm CSF was seen in association with significant improvement in PMD, OCT measures of papilloedema and quality of life measures [Wall, 2014].

The minimally clinically important change in the perimetric mean deviation adopted into clinical practice was established by the Neuro-Ophthalmology Research Disease Investigator Consortium (NORDIC) group and the IIH Treatment Trial (IIHTT). The investigators found a 0.71dB difference in the PMD between the two trial arms (comparing acetazolamide with placebo) that was clinically meaningful. The change of 0.71dB was interpreted as clinically meaningful as this was accompanied by significant changes in LP opening pressure, papilloedema (measured by OCT), general quality of life and visual related quality of life [Wall, 2014, Bruce, 2016].

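### The 90% power stated for PMD reproduces only as a one-sided slope comparison, so it is not shown to apply to the PMD estimand, which names no summary measure

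*Protocol*

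**What the plan says.** All references are to Protocol version 3.0 unless stated.

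- **Estimand.** Section 13.3.1.5 fixes the primary endpoint at one time: "Treatment difference in ICP measurement between Presendin and placebo at Week 24 for all patients who are randomised and start treatment". The initial secondary endpoint is worded differently: "Treatment difference in PMD between Presendin and placebo over 24-weeks for all patients who are randomised and start treatment". Section 13.3.1.6 repeats the same split. Neither section says whether the PMD difference is an average, a rate of change or an end value.
- **Target effect.** Section 13.2.1.1 (Perimetric Mean Deviation Power) takes its effect from an earlier trial, where "the improvement from baseline to 6-months in PMD was 0.71dB greater in the experimental arm than the control arm". Section 13.2.3.1 uses the same figure as its threshold: "The change of 0.71dB was interpreted as clinically meaningful".
- **Sizing.** The same power section counts on eight PMD measurements per patient, the first at baseline and the last at month 6. With an SD of 1.8 dB, a cited repeated-measures formula gives 142 patients in total for 90% power at a 5% level when the serial correlation is 0.4. For a weaker correlation it adds: "If the serial correlation parameter is as low as 0.3, the required sample size increases to 166". The section then divides 166 by 0.7 to get 237 and concludes that the planned 240 absorbs 30% missing data. It does not say whether the 5% is one- or two-sided, or which contrast the formula tests.

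**The concern.** PMD is one of the two outcomes for which section 13.2.1 says the study was powered, so its power statement matters. A repeated-measures formula can test a difference in slope or a difference in average level, and the two behave in opposite ways. The size for a slope rises as the correlation falls; the size for an average falls. The stated totals rise, which points to a slope. The estimand is a difference over 24 weeks of unspecified form, and the target is a month-6 change. If the formula tested something else, or at a different level from the planned test, the reader cannot carry the 90% across, and the assurance that 240 patients absorb the missing data may fail.

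**Working it through.** **Inputs (section 13.2.1.1, PMD power).** SD 1.8 dB; visits at 0, 0.5, 1, 2, 3, 4, 5 and 6 months; correlation ρ of 0.4 or 0.3, equal between all pairs of visits; effect 0.71 dB at month 6; power 90%; level 5%; 30% loss; 240 patients allocated 1:1. The two-sided level used below is an assumption, taken from the primary hypothesis in section 13.1, which is two-sided.

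**1. Reproducing 142 and 166.** For a comparison of slopes,

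n per arm = 2(z_α + z_β)² · SD² · (1 − ρ) / [Σ(t − t̄)² · d²].

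The visit times sum to 21.5 and their squares to 91.25, so Σ(t − t̄)² = 91.25 − 21.5²/8 = 33.47. The slope difference is d = 0.71/6 = 0.1183 dB per month, and 33.47 × 0.1183² = 0.4687.

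| Level | (z_α + z_β)² | ρ = 0.4: per arm, total | ρ = 0.3: per arm, total |
|---|---|---|---|
| One-sided 5% | 8.564 | 71.05, 142 | 82.89, 166 |
| Two-sided 5% | 10.507 | 87.17, about 174 | 101.70, about 204 |

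The one-sided row matches both stated totals. The same formula gives 68.8 and 96.3 per arm with the inputs of Protocol version 1.0 (SD 1.5; months 0, 2, 4, 6; ρ 0.5 and 0.3). Rounded, these are that version's stated totals of 138 and 192.

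**2. Alternatives that do not reproduce the totals** (ρ = 0.4 / 0.3):

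- Average over all eight measures, constant difference of 0.71 dB, n = 2(z_α + z_β)² · SD² · [1 + 7ρ]/(8 × 0.71²): 106 / 86 one-sided, 130 / 106 two-sided.
- Baseline-adjusted month-6 difference, n = 2(z_α + z_β)² · SD² · (1 − ρ²)/0.71²: 186 / 202 one-sided, 228 / 246 two-sided.
- Simple two-sample comparison: 222 one-sided, 272 two-sided.

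**3. The claim that 240 covers 30% loss.** One-sided: 166/0.7 = 237, as stated. Two-sided slope: 174.3/0.7 ≈ 249 at ρ = 0.4 and 203.4/0.7 ≈ 291 at ρ = 0.3. Both exceed 240.

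**4. Power with about 83 analysed per arm** (237 × 0.7 ≈ 166). Power = Φ(effect/SE − z_α).

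- Slope: SE = √[2 · SD² · (1 − ρ)/(33.47 × 83)] = 0.0374 / 0.0404; effect 0.1183.
- Week-24 difference, baseline-adjusted: SE = √[2 · SD² · (1 − ρ²)/83] = 0.256 / 0.267; effect 0.71.
- Average of the seven post-baseline visits, baseline-adjusted: SE = √[2 · SD² · ((1 + 6ρ)/7 − ρ²)/83] = 0.160 / 0.156. If the effect grows linearly to 0.71 dB at month 6, the average effect is 0.71 × (21.5/7)/6 = 0.363 dB.

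| Contrast (ρ = 0.4 / 0.3) | Two-sided 5% | One-sided 5% |
|---|---|---|
| Slope | 89% / 83% | 94% / 90% |
| Week-24 difference of 0.71 dB | 79% / 76% | 87% / 85% |
| Visit average, linear growth | 63% / 65% | 74% / 76% |

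If the difference were a constant 0.71 dB at every post-baseline visit, the visit average would have over 99% two-sided power.

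**The case against.** **The summary measure is for the SAP.** Section 13.3.1.6 closes by leaving details to the SAP, and section 13.2.1.1 mentions only a longitudinal method such as hierarchical regression. This stands as far as the model is concerned: a missing model specification would be no finding. It does not rescue the power figure, which the protocol fixes itself. A SAP can choose a contrast, but it cannot make a figure computed for one contrast and level apply to another.

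**A reader might infer that the protocol holds three incompatible definitions, or that the stated power belongs to the wrong estimand.** The documents do not support that. A slope of 0.71/6 dB per month and a month-6 difference of 0.71 dB are the same effect under linear growth. The wording over 24 weeks could also be read as a rate of change, which would match the calculation. What is shown is ambiguity and an unstated level, not a proven mismatch. Even on the slope reading, two-sided power at the stated sizes is 83%, not 90%.

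**A reader might infer that power could be anywhere from about 30% to 99%.** Those extremes come from assuming the full effect from week 2, when the slope test has 33%/29% and the visit average over 99%. The protocol states no PMD trajectory, so that range is not a property of the plan.

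**A reader might blame the whole shortfall on the choice of contrast.** Sidedness matters as much. At 83 per arm, moving from slope to Week 24 at one-sided 5% costs 5 to 7 points; moving Week 24 from one- to two-sided costs 8 to 9.

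**Second eyes.** Section 13.2.1.1 expects a modest uplift from eligible second eyes. This is fair, but it is not quantified and is not part of the stated 90%.

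**Conclusion.** The point holds in this form: 142 and 166 are slope sizes at a one-sided 5% level, and the protocol states neither feature, so its 90% is not shown to apply to the PMD estimand. The slope and the sidedness are inferred from the exact match, from the direction of change with correlation, and from the matching figures in version 1.0.

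At two-sided 5% the statement that 240 patients cover 30% loss fails even for the slope (about 249 and 291 needed). Two-sided power after that loss runs from 63% to 89% across the three contrasts under linear growth. The error is not always toward low power, because a sustained 0.71 dB difference would be more than adequately powered as an average.

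These figures assume SD 1.8, equal correlation of 0.3 to 0.4, one eye per patient, and 30% loss counted as whole patients, as the plan's own inflation does; partial follow-up would recover some power. Only appendix pages of version 4.0 are in the file, so whether the wording is still current could not be checked.

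**What to change.** 1. In sections 13.3.1.5 and 13.3.1.6, name one PMD contrast: slope, Week-24 difference or visit average. Week 24 would match the ICP estimand and the source of the 0.71 dB target, but choosing it is a trade-off and not the only acceptable answer.
2. In section 13.2.1.1 (PMD), state the contrast, the sidedness and the assumed course of the effect over time, and restate the power for that contrast. For a baseline-adjusted Week-24 difference at two-sided 5%, this is 79%/76% with about 83 per arm and 92%/89% with all 240 patients (ρ = 0.4/0.3).
3. Correct the claim that 240 covers 30% missing data, or state the one-sided level on which it depends.
4. Check first whether version 4.0 has already changed this text.

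The cost is wording and arithmetic, and a less favourable stated PMD power if the test is two-sided. No extra patients or procedures are needed.
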